11.2 Statistical methods

The primary analysis will be conducted including the intention-to-treat population [65–67]. A sensitivity analysis will be conducted including the per-protocol population, excluding patients with a major protocol violation (patients who did not receive the allocated trial intervention at all, patients who did not receive the trial intervention for at least two days in a row, treatment with PPI or H2RA without clinically indication and withdrawal from trial intervention). Patients transferred to another ICU will be considered discharged from the ICU.

The primary analysis of all dichotomous outcomes will compare the outcome at 90 days after randomisation in the two groups by binary logistic regression analysis with adjustment for stratification variables [68]: site and active haematological cancer

A secondary analysis will be performed adjusting for stratification variables together with other known major prognostic co-variables: age, baseline SOFA score, and type of admission (medical, elective surgery or emergency surgery).

Further details will be provided in a statistical analysis plan.

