Appendix 3.1 Charter for the independent Data Monitoring and Safety Committee (DMSC)

This amendment replaces Appendix 3 in the above-mentioned protocol.

Description: Cancellation of the second interim analysis (2500/3350 included patients).

Due to the inclusion rate the SUP-ICU trial Steering Committee, in full agreement with the DMSC, has decided to cancel the second interim analysis as the results (incl. 90-day follow-up) would be available only after the inclusion of the last trial patient.

The statement paper from the DMSC following the first interim analysis (1675/3350 included patients) supports this decision. The decision has been approved by relevant Danish authorities.

Stress Ulcer Prophylaxis in the Intensive Care Unit (SUP-ICU) trial: detailed statistical analysis plan

Comprehensive details of the SUP-ICU trial has been published elsewhere.¹ This statistical analysis plan was prepared before randomisation of patients and data collection in the SUP-ICU trial was completed. The analysis plan was approved by the SUP-ICU Steering Committee on September 22, 2016. Analysis of data for the primary publication will be conducted according to this plan.

Randomisation

Thirty-one sites in Denmark, Finland, the Netherlands, Switzerland and Norway are currently screening and randomising patients in the SUP-ICU trial. Some additional, 5-10 ICUs from the United Kingdom, Italy and Denmark are expected to participate. Copenhagen Trial Unit (CTU)²¹ is responsible for centralised and web-based 1:1 randomisation according to a computer-generated allocation sequence list, with two stratification variables (site and active hematologic cancer), and varying block size.

Blinding

The allocated trial medication will be masked to clinical staff caring for the patient, to the patient, investigators and outcome assessors. The statistical analysis of the trial will be blinded with the intervention groups coded as, e.g., X and Y. Based on this blinded analysis two conclusions will be drawn: one assuming X is the experimental group and Y is the control group, and another assuming the opposite. Two abstracts will be written and accepted by the SUP-ICU Steering Committee. After this, the intervention groups will be unmasked.

Sample size

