Because of the widespread use of SUP, no reliable control group for sample size estimation is available and producing reliable sample size estimations according to anticipated effects on GI bleeding is difficult.¹ As a consequence it has been necessary to calculate sample size estimations given that something may change if we withhold PPI until GI bleeding actually happens. Assuming a baseline 90-day mortality of 25%,² $\alpha=0.05$ (two-sided), and $\beta=0.1$, 3350 patients (2 x 1675) will be needed to show a 20% relative risk reduction (RRR) or increase (RRI) corresponding to a 5% absolute risk reduction or increase in the primary outcome measure. Trial Sequential Analysis^{22,23} of existing trials (n=16) has showed that 35% (1584 patients) of the required information size to

detect or reject a 20% RRR or RRI corresponding to 4575 patients has been accrued.⁸

Consequently, there is at least an information gap of around 3000 patients taking a 20% RRR in mortality as a clinically relevant effect size.

Outcome measures

Primary outcome

The primary outcome measure is all-cause mortality within 90 days after randomisation.

Secondary outcomes

1. Proportion of patients with one or more episodes of clinically important GI bleeding, pneumonia, *Clostridium difficile* infection or myocardial ischemia. The events are defined in appendix 1
2. Proportion of patients with one or more episodes of clinically important GI bleeding
3. Proportion of patients with one or more infectious adverse events (pneumonia or *Clostridium difficile* infections)
4. All-cause mortality within 1 year after randomisation
5. Percentage of days alive without use of life support (mechanical ventilation, circulatory support or renal replacement therapy) in the 90-day period
6. The number of patients with one or more serious adverse reactions (SARs) (defined in appendix 2)
7. A health economic analysis will be performed. The analytic details will be based on the result of the trial and specified prior to the analysis.

Pre-planned subgroup analyses

The primary outcome measure will be compared in the following pre-specified subgroups (definitions provided in appendix 2)

1. Shock at randomisation (y/n) (a hypothesised increased intervention effect in patients with shock at randomisation)
2. Mechanical ventilation at randomisation (y/n) (a hypothesised increased intervention effect in patients mechanically ventilated at randomisation)

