If multiple imputation is used, the primary result of the trial will be based on these data. A 'best-worst, worst-best case' scenario will be used as a sensitivity analysis to assess the potential impact of any pattern of missingness including that the data are missing not at random (MNAR criterion) for the trial results. In the 'best-worst-case' scenario it is assumed that all patients lost to follow-up in the experimental group have had a beneficial outcome (e.g. have survived) and all those with missing outcomes in the control group have had a harmful outcome (e.g. have not survived). Conversely, in the 'worst-best-case' scenario, it is assumed that all patients who were lost to follow up in the experimental group have had a harmful outcome; and that all those lost to follow-up in the control group have had a beneficial outcome.

The unadjusted, non-imputed analysis will also be presented.

General analytic principles

1. All main analyses will compare the two intervention groups in the intention-to-treat (ITT) population.²⁴⁻²⁶

The ITT population will be all patients randomised except:

- patients withdrawing consent for the use of data
- patients who were erroneously randomised AND who did not receive the trial intervention.²⁷

The conclusion of the trial will be based on the ITT analysis

2. In all analyses, a maximum level of 5% (two-sided) type 1 error will be regarded as statistically significant
3. Test-of-interaction will be applied for all subgroup analyses (logistic regression)

Statistical analyses

Trial profile

The flow of trial participants will be displayed in a Consolidated Standards of Reporting Trials (CONSORT) diagram. The number of participants fulfilling the inclusion criteria, the number of excluded participants and reasons for exclusion, and the number of participants included in the final analyses will be presented.

Primary outcome measure

The primary analysis will be a logistic regression analysis adjusted for stratification variables (site and presence of haematological cancer, y/n) of the ITT population. Results will be presented as odds ratios and relative risk ratios (relative risk ratios computed from odds ratios with covariates set to mean values for numeric covariates and the largest group for categorical).

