The secondary analysis will be a multiple logistic regression analysis of the ITT population adjusted for stratification variables and additionally differences in potential confounders: age, SOFA score at baseline, and type of admission (medical, elective surgery or emergency surgery). Intervention group and the stratification variable haematological cancer are regarded as fixed effects and trial site is regarded as random effects in the model. Furthermore, frequencies and percentages per group will be reported and an unadjusted Chi-square test for differences in the primary outcome will be provided.

Pre-defined subgroup analyses (see former section) of the ITT population will be conducted using logistic regression analysis adjusted for stratification variables.

A sensitivity analysis of the primary outcome measure including the per-protocol population will be conducted. The per-protocol population will be all randomised patients except those having one or more protocol violations defined as:

- Patients who did not receive the allocated trial intervention at all
- Patients who did not receive the trial intervention for at least two days in a row
- Patients who received treatment (open label) with PPI or histamine-2-receptor antagonists except for those receiving it according to the protocol (i.e. occurrence of GI bleeding after randomisation).
- Patients who withdrew from trial intervention, but consented to the use of data
- Monitoring revealed that one or more in- or exclusion criteria were violated

Secondary outcome measures

The secondary outcomes will only be analysed in the ITT population. The primary analysis of the binary secondary outcome measures will be a logistic regression analysis adjusted for the stratification variables (site and presence of haematological cancer). Results will be presented as odds ratios and relative risk ratios.

Furthermore, frequencies and percentages per group will be reported and an unadjusted Chi-square test for differences in the primary outcome will be provided.

The primary analysis of rate data ('Percentage of days alive without life support in the 90-day period') will be a generalized linear model (initially Poisson distribution, alternatively negative binomial).²⁸ If the assumptions for Poisson distribution or negative binomial distribution are not met, data will be analysed using the non-parametric Van Elteren test adjusted for site, but no other variables.²⁹

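### The primary model for 90-day mortality leaves out age, baseline SOFA and type of admission, an avoidable loss of efficiency rather than an error

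*Combined protocol and SAP*

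**What the plan says.** SAP, Statistical analyses, Primary outcome measure: "The primary analysis will be a logistic regression analysis adjusted for stratification variables". The variables are site and presence of haematological cancer, in the intention-to-treat population, and the trial's conclusion rests on that population. The secondary analysis of the same outcome further adjusts for "differences in potential confounders: age, SOFA score at baseline, and type of admission". Protocol section 11.2 has the same structure: "A secondary analysis will be performed adjusting for stratification variables together with other known major prognostic co-variables".

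The SAP's list of baseline variables includes age, elective or emergency surgery, and the values needed for SAPS II and SOFA. General analytic principles sets one threshold for every model: "In all analyses, a maximum level of 5% (two-sided) type 1 error will be regarded as statistically significant". The sample size (SAP, Sample size; protocol 11.1.1 and Appendix 11) is a comparison of two proportions. It assumes 25% baseline mortality and a 20% relative change, "corresponding to a 5% absolute risk reduction or increase in the primary outcome measure", with 90% power and 3350 patients. It makes no allowance for covariates.

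**The concern.** With concealed "centralised and web-based 1:1 randomisation", baseline imbalance arises by chance, so confounding is not the main reason to adjust. The main reason is precision: a baseline covariate that predicts death sharpens the treatment comparison. The protocol names three such covariates and the trial collects them, but the analysis that carries the conclusion does not use them.

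The gain is larger, in points of power, where the trial has less power. Protocol 11.2.3 and the SAP's Interim analysis section both say that effects on mortality below 15% may still be clinically relevant. The trial is sized for 20%, so at 15% its power is well under 90%.

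**Working it through.** **Inputs from the documents.** Two-sided alpha 0.05; 1:1 allocation; 1675 per arm; 25% versus 30% or 20%. Appendix 11 shows that the increase set the sample size (1671 per group, against 1461 for the reduction).

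**Input assumed.** R², the share of outcome variance that the three covariates explain beyond site and haematological cancer. The documents give no R², AUC or association with mortality, so a range of 0.05 to 0.20 is shown.

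**Step 1: reproduce the plan.** With p̄ the mean of the two risks,

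n per arm = [1.96·√(2p̄(1−p̄)) + 1.2816·√(p₁(1−p₁)+p₂(1−p₂))]² / (p₁−p₂)²

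For 25% versus 30%, p̄ = 0.275 and n = (1.2377 + 0.8080)² / 0.0025 = 1674, against 1675 stated. For 25% versus 20%, n = 1464, against 1461 in Appendix 11. At 1675 per arm, power is 90.0% and 93.4% respectively. The plan's figure stands.

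**Step 2: add the covariates.** Replace 1675 by 1675/(1−R²) in the same formula. A 15% relative effect means 25% to 28.75% or 25% to 21.25%.

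| Assumed R² | Effective n per arm | 25→30% | 25→20% | 25→28.75% | 25→21.25% |
|---|---|---|---|---|---|
| 0 | 1675 | 90.0% | 93.4% | 68.7% | 73.1% |
| 0.05 | 1763 | 91.4% | 94.5% | 71.0% | 75.2% |
| 0.10 | 1861 | 92.8% | 95.5% | 73.3% | 77.5% |
| 0.15 | 1971 | 94.0% | 96.4% | 75.7% | 79.7% |
| 0.20 | 2094 | 95.2% | 97.2% | 78.2% | 82.1% |

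An R² of 0.10 is worth 3350/0.90 − 3350 ≈ 372 extra patients.

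**Step 3: check by simulation.** 6000 trials per setting, 3350 patients each, logistic models with and without one normal prognostic score standing for the three covariates:

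| Assumed AUC | Matching R² | Gain, 25→30% | Gain, 25→20% |
|---|---|---|---|
| 0.65 | 0.054 | +1.1 points | +1.2 points |
| 0.70 | 0.098 | +2.8 | +2.2 |
| 0.75 | 0.156 | +4.2 | +3.6 |
| 0.80 | 0.230 | +6.3 | +3.8 |

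This agrees with Step 2 to within simulation error.

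**Step 4: what missing covariates would cost.** If 5% of patients leave the model for want of a SOFA component, the effective number is 0.95 × 1675/(1−R²). At R² 0.05 that is exactly 1675, so the gain is nil. At R² 0.10 the remaining gain is +1.5 points (25→30%) or +1.1 (25→20%). At R² 0.15 it is +2.9 or +2.2.

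**Step 5: the odds ratio.** The unadjusted odds ratio for 25% versus 30% is (0.30/0.70)/(0.25/0.75) = 1.29. With a covariate of AUC 0.70 in the model, the same marginal risks correspond to a conditional odds ratio of 1.32.

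**The case against.** The best defence is that this is a choice of emphasis. The plan meets its power target without the covariates, adjusting for the stratification variables is a coherent and referenced choice, and the fuller model is prespecified and will be reported. All of that stands, and it is why the point is not called an error. It is only a partial answer, because the 90% applies at a 20% relative effect.

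A reader might infer a firm gain of 3 to 5 points. The documents do not support that. A gain of that size needs an R² of about 0.11 to 0.19 in the direction of harm. For benefit, 5 points is not reached even at R² 0.25 (+4.5). Only the increment over the variables already in the model counts.

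A reader might also infer that the change is free. It is not:

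- SOFA covers six organ systems, and protocol 11.2.5 uses complete cases when less than 5% of data are missing. Above 5%, the SAP makes the multiply imputed result primary, so missing SOFA values alone could move the headline result onto imputed data.
- Appendix 4 counts an admission as medical when surgery took place more than a week before ICU admission, yet defines elective and emergency surgery by any operation in the same hospital stay. One patient can fit two categories.
- In Appendix 10 as printed, the mg/dl cut-offs for creatinine repeat those for bilirubin and do not scale with the µmol/l row, which needs checking before SOFA enters the primary model.

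Nor would the swap stop the two models from falling on opposite sides of p = 0.05. Both remain, along with an unadjusted chi-square test; the change settles only which leads. Finally, the remark about effects below 15% is made to explain why there is no futility stopping. It shows which effects the sponsors consider relevant, but it is not a power target.

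These objections limit the size of the claim and set conditions on the fix. They do not remove the precision gain.

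**Conclusion.** The point holds as a recommendation on efficiency. The primary model leaves unused three prognostic covariates that are already collected and already specified. At the design effect the loss is about 1 to 5 points of power in the direction of harm and about 1 to 4 in the direction of benefit; at a 15% relative effect it is about 2 to 9 points. These figures rest on an assumed R² of 0.05 to 0.20 beyond site and haematological cancer, take the two-proportion calculation as the baseline, and ignore the small effect of interim alpha spending. A reader should not infer that the trial is underpowered for its stated target, or that the planned model is invalid: the 90% figure reproduces, and the primary model respects the stratification.

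**What to change.** Before unblinding, amend the SAP (Primary outcome measure) and protocol section 11.2:

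1. Make the logistic model with site, haematological cancer, age, baseline SOFA and type of admission the primary analysis. Keep the stratification-only model as the sensitivity analysis.
2. Report a standardised (marginal) relative risk and risk difference, averaged over the trial's patients. The SAP's relative risk refers to one covariate profile, and adding covariates would tie it to a narrower one.
3. Prespecify a simple imputation for missing baseline covariates, based on baseline data only and blind to allocation, so that no patient leaves the primary analysis. State that values filled this way do not count towards the 5% missing-data threshold.
4. Make the three admission categories mutually exclusive, and check the creatinine row of the SOFA table.
5. Give precision as the reason for adjustment in place of confounding.

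No new data are needed. The cost is an amendment to two documents, with whatever prior review protocol section 1.7 requires, and an odds ratio that is conditional on more covariates. The first interim analysis has already taken place, so the amendment should state that it was made without knowledge of results by group.

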11.1.2 Power estimations for secondary outcomes

Power estimations are based on 3350 included patients, a risk of type 1 error of 5%, and a minimal clinically relevant difference as stated:

Clinically important GI bleeding: 46% power (baseline 3% -> 2% = 33% RRR) for showing or discarding a numbers-needed-to-treat (NNT) of 100.

Pneumonia: 85% power (baseline 20% -> 16% = 20% RRR) for showing or discarding a NNT of 25.

CDI: 53% power (baseline 10% -> 8% = 20% RRR) for showing or discarding a NNT of 50.

Myocardial ischemia: 29% power (baseline 5% -> 4% = 20% RRR) for showing or discarding a NNT of 100

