 - metastatic carcinoma
 - acquired immune deficiency syndrome (AIDS)
- Values for SAPS II and severity organ failure assessment (SOFA) scoring 24 hours prior to randomisation.

Daily during ICU admission

- Delivery of trial medication (y/n)
- Open label treatment with PPI/histamine-2-receptor antagonists (y/n)
- Invasive or non-invasive mechanical ventilation (y/n)
- Circulatory support (infusion of vasopressor/inotropes) (y/n)
- Any form of renal replacement therapy (y/n)
- Onset of pneumonia on this day (y/n)
- Treatment with antibiotics (enteral vancomycin, intravenous or enteral metronidazole, or enteral fidaxomicin) for suspected or proven *Clostridium difficile* infection on this day (y/n)
- Acute myocardial ischemia on this day (y/n)
- Enteral feeding on this day (y/n)
- Number of units of red blood cells transfused
- Overt GI bleeding episodes (hematemesis, coffee ground emesis, melena, haematochezia or bloody nasogastric aspirate) (y/n)
- Serious adverse reactions (SARs) (y/n) (appendix 2)

Bleeding form (only for patients with overt bleeding)

- Data on clinically important GI bleeding:
 - A spontaneous drop of systolic blood pressure, mean arterial pressure or diastolic blood pressure of 20 mmHg or more
 - start of vasopressor or a 20% increase in vasopressor dose
 - decrease in haemoglobin of at least 2 g/dl (1.24 mmol/l)
 - transfusion of 2 units of packed red blood cells or more
- Origin of GI bleeding confirmed (y/n)
- Verification of ulcer/gastritis/esophageal varices (y/n)
- Haemostasis achieved/attempted by endoscopy/open surgery/coiling (y/n)

Follow-up 90 days and 1 year after randomisation

- Death (y/n, if yes, date of death)

Missing data

If more than 5% of the observations are missing for any specific analysis that analysis will be conducted both as complete-case and using multiple-imputation based on chained equations. All variables in the specific analysis will be included in the multiple imputation as well as stratification variables (site and presence of haematological cancer), age, SOFA score at baseline, type of admission (medical, elective surgery or emergency surgery), SAPS II at baseline, renal replacement therapy at baseline, mechanical ventilation at baseline, shock at baseline, proportion of patients with clinically important GI bleeding, proportion of patients with one or more episodes of serious adverse events (pneumonia, *Clostridium difficile* infection and myocardial ischemia), and 90-day mortality.

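### The SAP's adjusted risk ratio is taken at a single covariate profile, so it is not the population RR the trial was sized on, and no adjusted risk difference is planned; this affects reporting only and is cheap to improve

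*Combined protocol and SAP*

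**What the plan says.** The SAP (Statistical analyses, Primary outcome measure) makes the primary analysis a logistic regression in the ITT population, adjusted for the two stratification variables, site and haematological cancer. Results are given as odds ratios and as "relative risk ratios computed from odds ratios with covariates set to mean values for numeric covariates and the largest group for categorical".

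The next paragraph, on the secondary analysis, states: "Intervention group and the stratification variable haematological cancer are regarded as fixed effects and trial site is regarded as random effects in the model". It sits with the secondary model but names the terms of the primary one, so it is unclear whether site is also random in the primary model.

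The SAP adds that "frequencies and percentages per group will be reported and an unadjusted Chi-square test for differences in the primary outcome will be provided". Under Missing data it also promises an unadjusted, non-imputed analysis. If more than 5% of observations are missing for an analysis, "that analysis will be conducted both as complete-case and using multiple-imputation based on chained equations", and "If multiple imputation is used, the primary result of the trial will be based on these data".

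For the binary secondary outcomes, "Results will be presented as odds ratios and relative risk ratios"; the conversion rule is neither repeated nor replaced.

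The target, under Sample size, is set on population risks: 3350 patients "will be needed to show a 20% relative risk reduction (RRR) or increase (RRI) corresponding to a 5% absolute risk reduction or increase", from a 25% baseline. Neither the SAP nor protocol section 11.2 plans an adjusted risk difference, and neither names a confidence interval for the RR.

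**The concern.** An odds ratio from a logistic model converts to different risk ratios at different baseline risks. Choosing one profile fixes that baseline. With site fixed, the profile is the largest site combined with the larger cancer category. The largest site was not known when the SAP was written: 31 sites were active and 5 to 10 more were expected. With site random, the bracket does not say which site value to use, so two programmers could report different RRs from the same fit.

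In both cases the headline adjusted RR is conditional, whereas the design effect is a ratio and a difference of population risks. What is at stake is how the result is expressed: whether the adjusted RR applies to the trial population, and whether the absolute scale of the target gets an adjusted estimate with an interval.

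**Working it through.** **Inputs from the documents.** Control risk 25%, target 20% or 30%, 1675 per arm, two-sided 5%, 90% power (SAP, Sample size; protocol 11.1.1 and Appendix 11). Sites: 31 plus 5 to 10, so 36 to 41 (SAP, Randomisation). Secondary baselines: protocol 11.1.2, for example pneumonia, "85% power (baseline 20% -> 16% = 20% RRR".

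**Assumptions, not in the documents.** Normal site effects with log-odds SD 0.2 to 0.4; haematological cancer in 5% of patients with OR 2 for death.

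**1. The plan's own figure.** n per arm = [1.960·√(2p̄(1−p̄)) + 1.2816·√(p0(1−p0) + p1(1−p1))]² / (p1−p0)². For 25% v 30%, p̄ = 0.275: (1.2377 + 0.8080)² / 0.0025 = 1674, against 1675 in the SAP and 1671 in Appendix 11. For 25% v 20% the result is 1464, against 1461. The target is therefore a comparison of population risks.

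**2. The conversion depends on the profile.** RR = OR / (1 − p + p·OR), with p the control risk at the profile. The design ORs are (0.20/0.80)/(0.25/0.75) = 0.75 and (0.30/0.70)/(0.25/0.75) = 1.286.

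| Profile control risk | OR 0.75 | OR 1.286 |
|---|---|---|
| 15% | 0.779 | 1.233 |
| 25% | 0.800 | 1.200 |
| 35% | 0.822 | 1.169 |

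**3. Size under site variation.** Model: logit(risk) = a + b·PPI + u, with u normal, mean 0. Solve a and b so that risks averaged over u are 25% and 20% (or 30%), then take the RR at u = −1, 0 and +1 SD.

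| Population RR | Site SD | Conditional OR | −1 SD | Average site | +1 SD |
|---|---|---|---|---|---|
| 0.80 | 0.2 | 0.749 | 0.791 | 0.798 | 0.807 |
| 0.80 | 0.4 | 0.744 | 0.779 | 0.793 | 0.811 |
| 1.20 | 0.2 | 1.288 | 1.214 | 1.202 | 1.190 |
| 1.20 | 0.4 | 1.296 | 1.231 | 1.209 | 1.183 |

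Example (SD 0.4, −1 SD): a = −1.1375, so the control risk is 17.69%, the PPI risk 13.79%, and the RR 0.779. The largest shift is 1.231 − 1.200 = 0.031.

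**4. Cancer term.** Taking the RR in the no-cancer category moves the average-site values (SD 0.4) from 0.793 to 0.791 and from 1.209 to 1.213.

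**5. Sampling error.** SE(log RR) = √(0.80/(0.20·1675) + 0.75/(0.25·1675)) = 0.0646, giving a 95% CI of 0.70 to 0.91. For RR 1.20 the SE is 0.0564 and the CI 1.07 to 1.34. A 5-point RD has a CI of about 2 to 8 points.

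**6. Event types in protocol 11.1.2** (SD 0.4, within 1 SD). Pneumonia: 0.80 reads 0.783 to 0.809. CDI: 0.791 to 0.804. Myocardial ischaemia: 0.796 to 0.802. GI bleeding: 0.667 reads 0.663 to 0.668. No baseline is given for the composites or 1-year mortality; at an assumed 30% to 40% risk, 0.80 reads 0.77 to 0.82.

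**7. Crude against standardised.** Allocation is 1:1 in blocks within the same strata the model adjusts for, so the two should nearly coincide. In simulated trials of 38 sites with 88 patients each (assumed blocks of 4 and 6, site SD 0.4, cancer as above, RR about 0.80), crude and standardised RR differed by no more than 0.005 to 0.007 in 95% of trials, and the RDs by no more than about 0.14 points. The sampling SD of the RR was about 0.05.

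**8. Sparse outcomes.** 3350/41 = 82 and 3350/36 = 93 patients per site. At 2.5% bleeding risk, the midpoint of 3% and 2%, that is about 2 events per site. The chance of none is 0.975^82 ≈ 13% to 0.975^93 ≈ 9%.

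**The case against.** The strongest reply is that nothing in the plan is wrong. An RR at a declared profile is a legitimate summary, and the 20% and 5 points are design assumptions, not a declared estimand. The percentages per group and the unadjusted analysis already let a reader compute a crude RR and RD, with intervals from the counts, and step 7 shows these will almost equal the standardised values. The site and cancer parameters are assumed, and the shift is small beside sampling error. For sparse outcomes with fixed site effects, sites without events would make ordinary delta-method intervals unreliable.

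Most of this stands, and it limits the point to an optional improvement. What remains is that the headline adjusted RR depends on which site enrols most, or on an unstated site value. The crude figures also do not come from the pre-specified primary model or, where imputation is used, from the data on which the primary result rests.

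A reader might infer that the trial's absolute effect will be distorted, because a risk difference computed at one profile moves more than the RR does. The documents do not support that: no single-profile risk difference is planned.

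**Conclusion.** The point holds as a reporting improvement. The planned adjusted RR is conditional on one profile, the target is on the population scale, and no adjusted RD with a CI is planned. With site SDs of 0.2 to 0.4 the shift is below 0.01 at an average site and up to about 0.03 if the largest site is within 1 SD, well inside the sampling CI. For GI bleeding it is negligible. These sizes rest on the assumed site spread.

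Two stronger readings are tempting but unsupported. One is that the primary conclusion is at risk: the test is on the treatment coefficient, so type I error, power, the OR and the ITT conclusion are untouched, and the gap vanishes at OR = 1. The other is that the RR would be further off in the secondary model with age, SOFA and admission type: the SAP promises no RR for that model.

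The gain is a headline adjusted RR that applies to the trial population, and an RD with an interval.

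**What to change.** Replace the bracketed rule with marginal standardisation. From the pre-specified logistic model, predict each ITT patient's risk under PPI and under placebo, average each over all ITT patients, and report the ratio and the difference of the averages with 95% CIs (delta method or bootstrap). Leave the model and its test as they are.

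- State whether site is fixed or random in the primary model. If random, say whether site effects are integrated out or predicted per site. The choice moves the RR by less than 0.003 under the assumptions above, so either will do if named.
- Under multiple imputation, standardise within each imputed data set and pool log RR and RD by Rubin's rules.
- Use the same rule for binary secondary outcomes with enough events. For sparse ones (GI bleeding, SARs), use a random site effect or bootstrap CIs, or give the crude RR and RD with CIs.

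Cost: a few SAP sentences and some extra programming, slightly more with a random site effect or imputed data. No new data, and no change to the sample size.
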